### **6.2.5 Columbia Suicide Severity Rating Scale**

The Columbia suicide severity rating scale (C-SSRS) is a questionnaire used for suicide assessment. At screening, the “Screening/Baseline” version is to be used to determine eligibility. During all subsequent visits, the “Since last visit” version is used to monitor on-study suicidal ideation and behavior after the initial assessment. Analysis will mainly focus on two aspects: suicidal ideation and suicidal behavior and they will be derived for each subject as follows using the “Since Last visit” version:

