10. Subject has a history of suicide attempt or suicidal behavior within the last 12 months, or has suicidal ideation within the last 12 months (a response of "yes" to questions 4 or 5 on the suicidal ideation portion of the Columbia-Suicide Severity Rating Scale [C-SSRS]), or who is at significant risk to commit suicide, as judged by the Investigator at Screening and at the time of Visit 3 (Randomization).
11. Subject has clinically significant abnormalities in clinical chemistry, hematology, or urinalysis, or a serum creatinine > 1.5x the ULN at Screening. These assessments may be repeated once, after a reasonable time period at the Investigator's discretion (but within the Screening period).
12. Subject has aspartate aminotransferase (AST) or alanine aminotransferase (ALT)  $\geq$  1.5 times the upper limit of the reference range at Screening. These assessments may be repeated once, after a reasonable time period at the Investigator's discretion (but within the Screening period).
13. Subject has a positive test for hepatitis B surface antigen (HBsAg), hepatitis A virus antibodies (immunoglobulin M) (anti-HAV [IgM]) or hepatitis C virus antibodies (anti-HCV) at Screening or has history of a positive test for human immunodeficiency virus type 1(HIV-1) and/or type 2 (HIV-2).
14. Subject has a resting systolic blood pressure > 180 mmHg or < 90 mmHg, and/or a sitting diastolic blood pressure > 100 mmHg at Screening. These assessments may be repeated once, after a reasonable time period at the Investigator's discretion (but within the Screening period).
15. Subject has a clinically significant abnormality on 12-lead electrocardiogram (ECG) at Screening or Visit 3 (Randomization). If the ECG is abnormal, based on the Investigator's judgment, an additional ECG can be carried out. If this also gives an abnormal result, the subject must be excluded.

16. Subject has a history of myocardial infarction (within 6 months of Screening), unexplained syncope, cardiac arrest, unexplained cardiac arrhythmias or torsade de pointes, structural heart disease or a family history of Long QT Syndrome.

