## 12.6 Questionnaires

Questionnaire	Frequency/Visit
Daily Average Pain NRS Score	Daily from Visit 2 onwards, at home, until Visit 7 by subject. Every attempt should be made by the subject to enter the daily NRS score at a consistent time in the evening throughout the study.
[REDACTED]	[REDACTED] [REDACTED]
M.I.N.I.	Visit 1 at clinic by site personnel on paper
HADS	Visit 1, Visit 3 and Visit 6 at clinic by subject
C-SSRS	Visit 1, Visit 3, Visit 4, Visit 5, Visit 6 and Visit 7 at clinic by site personnel.
CMSI	Visit 2 by the subject on the ePRO device
PGIC	Visit 4, Visit 5, Visit 6 and Visit 7 at clinic by subject
PGIS	Visit 3, Visit 4, Visit 5, Visit 6 and Visit 7 at clinic by subject
[REDACTED]	[REDACTED]
FIQR	Visit 1, Visit 3, Visit 4, Visit 5, Visit 6 and Visit 7 at clinic by subject
[REDACTED]	[REDACTED]
[REDACTED]	[REDACTED]
[REDACTED]	[REDACTED]

For the daily questionnaires the subject will receive an e-diary that can be taken home. The subject should take the e-diary to the clinic for each study visit. For the questionnaires to be completed at the site the subject will use the tablet that is available at the site (except for the M.I.N.I.).

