- z) Columbia Suicide Severity Rating Scale (C-SSRS). Questionnaire will be facilitated by the Principal Investigator/Site staff, as appropriately trained, at screening, randomization, weeks 2, 4, 8/EOT, and week 10/follow up visits.
- aa) Subject Training Materials are to be distributed and reviewed during the screening period.
- bb) Subjects will begin study drug dosing on day 1 of the randomization visit.
- cc) (Serious) Adverse Events will be collected from the time of signing the informed consent through 4 weeks post-last dose.

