### 7.2.3.2 Fibromyalgia and Targeted Medical History

Fibromyalgia and targeted medical history will be summarized by descriptive statistics for the following variables listed in [Table 16](#). This will be done for all randomized subjects, the SAF, FAS and PPS by treatment group and ‘Total’ over all treatment groups.

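### C-SSRS Baseline comes from the Since Last Visit form, so history recorded only at Screening is missing from the baseline tables and the suicidal behavior row is near zero by design

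*SAP*

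**What the plan says.** SAP 6.2.5 assigns the two versions of the form by visit: "At screening, the “Screening/Baseline” version is to be used to determine eligibility", and then "During all subsequent visits, the “Since last visit” version is used to monitor on-study suicidal ideation and behavior after the initial assessment". It goes on to say of suicidal ideation and suicidal behavior that "they will be derived for each subject as follows using the “Since Last visit” version". Table 14 applies this to Baseline, the treatment-period visits and the follow-up period, and gives no different source for Baseline.

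The C-SSRS is administered "at screening, randomization, weeks 2, 4, 8/EOT, and week 10/follow up visits" (SAP Table 1). Protocol 12.6 gives the same schedule as "Visit 1, Visit 3, Visit 4, Visit 5, Visit 6 and Visit 7 at clinic by site personnel", so there is no assessment at Visit 2. SAP 6.2 and the footnote to SAP Table 30 take Baseline for safety variables as the last assessment on or before the first dose day.

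For reporting, SAP 7.5.7 plans counts by time point and arm and the worst finding per period. It lists every C-SSRS assessment for subjects with at least one suicidality event. SAP 7.2.3.2 says "Fibromyalgia and targeted medical history will be summarized by descriptive statistics for the following variables" in Table 16, and that table includes four C-SSRS items.

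**The concern.** A baseline row normally tells the reader what subjects brought into the trial. Here the form that asks about history is used to decide eligibility and is then given no place in the derived variables. The form that feeds Baseline asks only about the weeks since Screening.

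Relevant history is plausible in this population. Exclusion criterion 6 admits subjects with treated, stable major depression, and criterion 9 admits HADS depression scores up to 14. Criterion 10 excludes a subject who had suicidal behavior in the last 12 months or who "has suicidal ideation within the last 12 months" on questions 4 or 5. Ideation limited to questions 1 to 3, and events older than 12 months, do not exclude a subject unless the investigator judges the risk significant.

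Protocol 5.4 gives CNS penetration of the drug as the reason for prospective suicidality assessment. With about 89 subjects per arm, events may be few, and each will be read closely. A reader will want to know whether an on-treatment finding is a recurrence and whether the arms started alike. The planned tables answer neither question.

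**Working it through.** No power, alpha or event-rate calculation bears on this point, and the plan gives no figure to reproduce. The check is to set the rules side by side.

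**Step 1: which form is Baseline.** The only pre-dose C-SSRS assessments are at Screening (Screening/Baseline version) and at Randomization on Day 1 (Since Last Visit version). The rule in SAP 6.2 selects the later one. The rule in SAP 6.2.5 selects the Since Last Visit version. Both lead to the Randomization form.

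**Step 2: what that form covers.** It covers the time from Screening to Day 1. Protocol 2.2.1 says the Screening period should in general not exceed 42 days, so Baseline looks back at most about 42 days.

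**Step 3: trace the cases.**

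| Screening form | Day 1 form | Baseline under the SAP |
|---|---|---|
| Yes | No | No; the Screening finding is not in the row |
| Yes | Yes | Yes; the subject is shown correctly |
| No | Yes | Yes |
| Yes | Missing | Unresolved |

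In the last case SAP 6.2 points to the Screening form, while 6.2.5 names only the other version. The note to Table 14 rules out imputing missing answers, so nothing turns this case into No.

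**Step 4: effect of eligibility.** Protocol 2.2.1 has the C-SSRS obtained and reviewed before randomization at Visit 3. An interval of up to 42 days that ends on Day 1 lies inside the 12-month exclusion window of criterion 10. A Yes for suicidal behavior on the Day 1 form therefore makes the subject ineligible. Barring protocol deviations, the Baseline behavior row is zero in both arms. For the same reason, Baseline ideation can reflect only questions 1 to 3 within those weeks.

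**Step 5: other outputs.** Laboratory data (SAP 7.5.3) and ECGs (SAP 7.5.5) have shift tables from baseline. The C-SSRS has none, and no definition of new-onset suicidality is given. The Baseline row beside the on-treatment rows is the only tabulated before-and-after view. The listing in 7.5.7 should show the Screening record of a subject who has an event, but it gives no count or denominator by arm. If an event means one derived under 6.2.5, a subject whose only positive answer is on the Screening form is neither tabulated nor included in that listing.

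**Step 6: Table 16.** It repeats the four item names from Table 14 and does not say which form supplies them. That it follows Table 14 is likely but not stated.

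**The case against.** The strongest case against is that no safety comparison changes. On-treatment rows use on-treatment answers only, both arms follow the same rule, and SAP 7.5 plans no hypothesis tests on safety. Using one version of the form from Day 1 onward also keeps the baseline and post-baseline intervals similar in length. The Screening record should be visible in the listing for any subject with an on-treatment event. History is also captured elsewhere: the protocol collects psychiatric history (5.2.2), and Table 16 tabulates major depressive disorder. A baseline defined as the worst answer ever given would bring the opposite fault, since a remote episode could make a genuine on-treatment event look pre-existing.

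Most of this stands. It limits the point to description and argues against merging the two pre-dose periods into one Baseline value. It does not rescue the Baseline behavior row, which carries almost no information under the stated rules, or the C-SSRS rows under a medical-history heading if they come from the same derivation. Listings of individual cases also cannot show whether the arms were balanced on prior suicidality.

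A reader might go further and infer that every Screening-form finding is shown as No and that on-treatment events will be reported as new. The documents support neither. The first fails when the finding is reported again before Day 1 and is undetermined when the Day 1 form is missing. The second fails because no new-onset or shift output is planned.

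**Conclusion.** The point holds as a descriptive weakness that is worth correcting. Under the SAP's own rules, C-SSRS Baseline describes the Screening-to-Day 1 interval. History found only on the Screening form is left out of the Baseline row, and the behavior row is near zero by design. The planned tables therefore cannot show pre-treatment suicidality, imbalance in it between arms, or recurrence as against new onset.

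The number of subjects affected cannot be derived. The documents give no rate of Screening-form ideation and no rate at which it persists to Day 1. A reader might try to size the loss by comparing 42 days with 12 months. That comparison fails because the two windows follow one another and neither contains the other. Twelve months is also the eligibility window for behavior and for ideation questions 4 and 5. The documents do not state the recall period for questions 1 to 3, and Protocol 5.4.6 says that recall differs by question. Nor do the documents show that a between-arm signal would be created or hidden, since on-treatment counts by arm are unaffected.

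The conclusion assumes that 6.2.5 means what it says for the Baseline row. For Table 16 it also assumes that those items follow Table 14.

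**What to change.** - **Table 16:** report suicidal ideation and behavior from the Screening/Baseline form, labelled with the recall period that form collects. Show this separately from the Randomization Since Last Visit result.
- **SAP 6.2.5 and Table 14:** state which form defines Baseline and what is used when the Day 1 form is missing.
- **SAP 7.5.7:** add, by arm, the number of subjects whose worst on-treatment category is new or worse than all pre-dose C-SSRS data from both forms.

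The cost is SAP wording and one extra descriptive table. Both forms are already collected on the tablet (Protocol 5.4.6), so no new assessment is needed. The drawback is that remote history may make some on-treatment events count as pre-existing. Showing the two pre-dose periods separately lets the reader see where that happens.

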**Table 14 Derivation of Columbia Suicide Severity Rating Scale (C-SSRS) Scores**

Analysis Time Point	C-SSRS Item	Derivation
Baseline	Suicidal ideation	A “yes” answer to any one of the following five questions from suicidal ideation section on the C-SSRS. 1. Wish to be dead 2. Non-specific active suicidal thoughts 3. Active suicidal ideation with any methods (not plan) without intent to act 4. Active suicidal ideation with some intent to act, without specific plan 5. Active suicidal ideation with specific plan and intent
Treatment period Week 2, Week 4, Week 8, EOT, Overall double-blind treatment period		If a subject answer “yes” to more than one suicidal ideation question within a visit window as an analysis time point (Section 7.11.5.3 Table 30) the worst-case response (i.e. the highest) will be used in any summaries.
Follow-up period Week 10 Overall follow-up period	Suicidal behavior	A “yes” answer to any one of the following five questions from suicidal behavior section on the C-SSRS. 6. Preparatory acts or behavior 7. Aborted attempt 8. Interrupted attempt 9. Actual attempt 10. Completed suicide If a subject answer “yes” to more than one suicidal behavior question within a visit window (Section 7.11.5.3 Table 30), at an analysis time point the worst-case response (i.e. the highest) will be used in any summaries.
	Suicidal ideation or behavior	A “yes” answer to any one of the above ten suicidal ideation or behavior questions on the C-SSRS.
	Self-injurious behavior without suicidal intent	A “yes” answer to the following question from suicidal behavior section on the C-SSRS: “Has subject engaged in Non-Suicidal Self-Injurious Behavior?”

There will be no imputation for missing answers on questions.

### **6.3 Pharmacokinetic Variables**

Pharmacokinetic (PK) sampling will occur on Day 1 in the clinic at approximately 1 to 4 hour(s) after dosing and once at Weeks 2, 4 and 8 /EOT. PK samples at weeks 2, 4, and 8/EOT should be evenly split between the following 3 sampling windows: before dosing, 1-4 hours post dose and >4 hours post dose. Time of the last dose and time of sample collection will be captured in the electronic Case Report Form (eCRF) during these visits, as well as the date and time of the last meal in relation to that dose will be captured in the eCRF.

Analysis of ASP8062 and any metabolites (if applicable) will be performed using a validated method at a bioanalytical laboratory specified by the Sponsor.

## 6.4 Other Variables

### 6.4.1 Exposure

For each subject, duration of exposure (defined as length of time on 8 weeks of treatment period) will be calculated in days, using the following formula:

- Duration of exposure = Date of last dose of study drug – Date of first dose of study drug +1,

where the date of first dose of study drug and the date of last dose of study drug are defined as the first study drug dosing date and the last study drug dosing date, as captured in the eCRF. Imputed dates for the first or last dose of study drug may be used to calculate exposure (Section 7.11.1).

### 6.4.2 Percent Overall Compliance

Subjects will be instructed to take 2 tablets once per day, one tablet of 25 mg and 1 tablet of 5 mg.

Percent tablet-count compliance is defined as the number of tablets taken divided by the total number of tablets that should have been taken:

$$\frac{\text{Total number of tablets actually received during 8 weeks of treatment period}}{\text{Total number of tablets planned to receive during 8 weeks of treatment period}} \times 100$$

Where,

- Total number of tablets actually received during 8 weeks of treatment period = total number of tablets dispensed during 8 weeks of treatment period – total number of tablets returned during 8 weeks of treatment period.
- Total number of tablets planned to receive during 8 weeks of treatment period = 2 x duration of exposure. Duration of exposure will be calculated as described in Section 6.4.1

Double-blind study drug compliance for the entire double-blind treatment period will be calculated for subjects whose total number of tablets taken and the complete date of the first dose and the last dose of double-blind study drug are known.

### 6.4.3 Previous and Concomitant Medication

- Previous and concomitant non-medication therapy

A previous non-medication therapy (screening/wash-out) is defined as any non-medication therapy administered up to the last day of screening/washout (i.e., prior to the baseline diary run-in).

A previous non-medication therapy (baseline diary run-in) is defined as any non-medication therapy administered after the last day of screening/washout and before the first dose of double-blind study drug.

A concomitant non-medication therapy (double-blind treatment period) is defined as any non-medication therapy administered between the first dose (inclusive) of double-blind study drug and the last dose of double-blind study drug (inclusive).

A concomitant non-medication therapy (follow-up period) is defined as any non-medication therapy administered after the last dose of double-blind study drug.

- Previous and concomitant medication

A previous medication (screening/wash-out) is defined as any medication taken up to the last day of screening/washout (i.e., prior to the baseline diary run-in).

A previous medication (baseline diary run-in) is defined as any medication taken after the last day of screening/washout and before the first dose of double-blind study drug.

A concomitant medication (double-blind treatment period) is defined as any medication taken between the first dose (inclusive) of double-blind study drug and the last dose of double blind study drug (inclusive).

A concomitant medication (follow-up period) is defined as any medication taken after the last dose day of double-blind study drug.

#### **6.4.4 Time Since Onset of Fibromyalgia Symptoms and Time Since Diagnosis**

- Time since onset of FM symptoms (years) = (Informed consent date -date FM symptoms started + 1)/365.25
- Time since FM diagnosis (years) = (Informed consent date – date of FM diagnosis + 1)/365.25.

Imputed dates for the date FM symptoms started and FM diagnosis may be used to calculate both of these endpoints as described in Section 7.11.1

#### **6.4.5 Mini-International Neuropsychiatric Interview**

The M.I.N.I. International Neuropsychiatric Interview (M.I.N.I 7.0) is a short, structured diagnostic interview administered by trained personnel. The instrument captures the major Axis I psychiatric disorders in Diagnostic and Statistical Manual of Mental Disorders (DSM-V) and International Statistical Classification of Diseases and Related Health Problems (ICD-10). Each module begins with screening questions that are answered yes or no. A negative response in the screening algorithm advances the interview to the next module, whereas a positive response will prompt additional questions that ask subjects to characterize behavior with “yes” or “no” responses. The final number of YESs or NOs allows the coding a final evaluation per module by Yes/No answer (according to time recall) or severity (according to module): current, in early remission and in remission. The M.I.N.I. 7.0 will be completed at Screening and any diagnosis identified from the M.I.N.I will be captured in the eCRF.

#### **6.4.6 Widespread Pain Index and Symptom Severity Scale score**

The Widespread Pain Index (WPI) and Symptom Severity (SS) scale score will be completed by the clinician on a tablet device during the Screening visit.

The WPI is a checklist of 19 non-articular body parts classified in 5 body regions. The body parts are checked if pain/tenderness is observed. The WPI global score is the sum of body parts checked as presence of pain and ranges from 0 to 19.

The SS Scale is comprised of two parts:

- First part: evaluation of 3 key-symptoms (fatigue, waking unrefreshed and cognitive symptoms) over the past week. The severity of these symptoms will be measured on a 4-point response scale (from 0 = no problem to 3 = severe).

The score for the first part is the sum of the item scores and ranges from 0 to 9.

- Second Part: presence evaluation (1=presence and 0=absence) of 3 other somatic symptoms (headaches, pain/cramps in lower abdomen and depression) during the previous 6 months.

The score for the second part is the sum of the item scores and ranges from 0 to 3.

The SS Scale score is the sum of the first and the second part scores and ranges from 0 to 12.

#### **6.4.7 Complex Medical Symptoms Inventory**

The Complex Medical Symptoms Inventory (CMSI) is designed to aid clinicians in collecting information from fibromyalgia patients regarding their disease-specific symptoms and to characterize the diagnosis. The inventory contains 2 parts: a symptom checklist to be completed by patients, and a diagnostic inventory completed by the clinician. In this study, only the symptom checklist will be utilized.

The symptom checklist contains 39 items (males) or 41 items (females). For each symptom question, subjects mark a box to indicate if the symptom: 1) has occurred for at least 3 months in the past year, and/or 2) has occurred for a 3-month period during their lifetime. Only the boxes that apply should be checked. The CMSI will be completed on the tablet device by the subject at Baseline Diary Run-In (Visit 2). The CMSI total score is the sum of the number of items that the subject checks as either occurring for at least 3 months in the past year and/or has occurred for a 3-month period during their lifetime. The CMSI total score at baseline will be calculated and ranges from 0 to 39 for males and 0 to 41 for females. Baseline is defined as the last assessment on or prior to the first dose day (Day 1) of double-blind study drug.

## **7 STATISTICAL METHODOLOGY**

### **7.1 General Considerations**

For continuous variables, descriptive statistics will include the number of subjects (n), mean, standard deviation (SD) and/or standard error (SE), median, minimum and maximum. When needed, the use of other percentiles (e.g. 10%, 25%, 75% and 90%) will be mentioned in the relevant section. Frequencies and percentages will be displayed for categorical data.

Percentages by categories will be based on the number of subjects with no missing data, i.e. will add up to 100%.

Summaries based on FAS and PPS (e.g. disposition, baseline and efficacy data) will be presented by planned treatment group, unless specifically stated otherwise. Safety analysis and other summaries based on SAF will be presented by actual treatment received. For summaries which present both absolute values over time and change from baseline values over time the number of subjects used to calculate the descriptive statistics will be those who have non-missing data at each analysis visit and at baseline. For endpoints which include mBOCF, LOCF or mLOCF imputation the descriptive statistics will be calculated after the imputation has been performed.

Unless otherwise specified, statistical comparisons will be made using one-sided tests at the  $\alpha=0.05$  significance level and two-sided 90% confidence intervals (CIs) will be presented when applicable. When two-sided p-values are presented statistical comparisons will be made using an  $\alpha=0.1$  significance level.

The pooled site will be used in all statistical models that include the “center” as a factor. The pooling sites algorithm is provided in Section 7.11.6.

All data, including observed and derived data, will be presented in subject data listings.

All data processing, summarization, and analyses will be performed using SAS® Version 9.3 or higher on Unix. Specifications for table, figures, and data listing formats can be found in the TLF specifications for this study.

[REDACTED]

[REDACTED]

[REDACTED]

[REDACTED]

